## 5.2 Handling of Study Interventions

Alteplase (recombinant human tissue-type plasminogen activator) is a sterile powder for reconstitution with Sterile Water for injection. The reconstituted preparation results in a colorless to pale yellow transparent solution containing Alteplase 1mg per ml at approximately pH 7.3. The Alteplase will be prepared in a sterile syringe labeled for investigational use. See the Alteplase Package Insert for additional product information. See MOP Chapter 19 (Pharmacy Manual) for additional instructions regarding Alteplase and flush preparation and labelling.

The following measures will be taken for storage and accountability of the investigational product:

1. The investigational product is Alteplase, which is stored refrigerated at 2-8° (36-46°F). The refrigerator temperature must be monitored and the documentation logs must be maintained for the time period that investigational product is stored at the site.

2. Accountability for each box of Alteplase will be emphasized during the training sessions.
3. Investigational product should be stored in a secure area according to local regulations. It is the responsibility of the investigator to ensure that investigational product is only dispensed to study subjects. The investigational product must be dispensed only from the official study sites by authorized personnel according to local regulations.
4. The investigational product shall be dispensed in accordance with the authorized prescriber's prescription.
5. A drug accountability form will be provided to the site. This form will be used to document all investigational product transactions (i.e., receipt of drug, dispensings, wasted doses, etc.). This documentation will be maintained at the site however, copies will be requested periodically and at the end of the study.
6. Drug accountability will be checked remotely and/or during on-site monitoring visits by review of drug accountability logs and other study documentation.
7. All unused investigational product may be discarded on site according to each site-specific policy for disposal of pharmaceutical waste. Prior to disposal of the drug, the Coordinating Center Study Pharmacist must receive a copy of the center's policy for study drug disposal (pharmaceutical waste) and documentation of the drug to be discarded.
8. The total of amount of Alteplase administered will be recorded on the source documents and case report forms.

### 5.3 Concomitant Interventions

- 5.3.1. **Required Interventions.** Intraclot administration of 1mg of rt-PA followed by 3 ml of flush every eight hours for up to nine doses.
- 5.3.2. **Permitted Interventions.** Study center standard of care policies may govern the use of low molecular weight, fractionated and unfractionated heparins for DVT prophylaxis during the acute treatment and follow-up periods. Heparin flushes of systemic lines are also permitted. Use of enoxaparin for DVT prophylaxis in the ICU at the usual doses of 30 mg sc Q12 h or 40 mg sc QD is permitted as long as the patient has good renal function (creatinine clearance of > 30 ml/min) or does not have an unusually low body weight (< 45 kg).

Including but not limited to NovoSeven, fresh frozen plasma, plasma concentrate and vitamin K, are permitted singly or in combination (but not required) for reversal of anticoagulation.

- 5.3.3. **Prohibited Interventions.** During the study period (randomization through the 12 month visit), avoid enoxaparin at therapeutic doses  $\geq 1.0$  mg/kg sc Q12 h.

After the day 30 follow up visit other antithrombotic and antiplatelet agents such as Coumadin (warfarin) and Dabigatran, glycoprotein IIb/IIIa inhibitors (eptifibatide/Integrilin, abciximab/Reopro, tirofiban/Aggrastat), ASA, clopidogrel/Plavix may be administered.

The use of Urokinase, Retevase, Desmoteplase, Tenecteplase or any other thrombolytic agent (other than the study agent) administered via any brain catheter is prohibited. Clogged catheters should be treated with normal saline flushes.

- 5.3.4. **Precautionary Interventions.** If any brain catheter (ICH or IVH, if present) needs to be replaced or repositioned during dosing, wait 24 h after the most recent dose to perform the procedure. A stability CT scan must then be done  $\geq 6$  h after all placements/repositioning to confirm correct placement, clot stability, and absence of significant blood along the catheter tract. Once these are confirmed by the site and Neurosurgical Center, dosing may restart.

If a subject experiences asymptomatic bleeding (ICH expansion  $< 5$  cc, IVH expansion as assessed by  $< 2$ mm increase in 2 out of 3 ventricular regions, or catheter tract hemorrhage that is  $\leq 5$  mm in the largest diameter), continue the dosing and CT schedule. If the bleeding is larger than these thresholds, with or without mass effect, the next scheduled dose is held and a repeat CT scan is done  $\geq 24$  h after the previous dose. If the ICH, IVH, and catheter tract hemorrhage are stable (i.e., has not further grown by  $> 5$  mm), then dosing may restart.

Particular caution needs to be observed with renal dialysis patients receiving rt-PA. Because this group of patients can experience wide variations in blood pressure with dialysis attendant cardiac volume changes, attention to long-term and intra-procedure blood pressure control is important. Similarly, attention to regional anti-coagulation management is important.

Consider administering platelets to eligible patients who are on antiplatelet therapy (Plavix, aspirin, etc.) at the time of symptom onset. Platelet counts should be closely monitored in this population.

#### 5.4 Adherence Assessment

Protocol adherence will be determined by review of data recorded on the case report forms that has been verified through comparison with the medical record and other source documentation. Compliance and treatment fidelity will be reported overall and by center to the DSMB at each scheduled review session. Study centers demonstrating poor protocol compliance will be retrained and, if necessary, replaced.

6 CLINICAL AND LABORATORY EVALUATIONS6.1 Schedule of Evaluations

	Screening / Baseline	Day 1 (day of randomization)	Day 2	Day 3	Days* 4 - 6	Day 7	Day 30 ± 7 days	Day 90 ± 7 days	Day 180 ± 14 days	Day 270 ± 14 days	Day 365 ± 14 days
Diagnostic CT	X										
Informed consent	X										
Stability CT (6 hours after diagnostic CT)	X										
Pregnancy test	X										
Medical History/ Review of Systems	X										
CTA (MRA)/MRI	X					Day 7-10 ± 1 day X (MRI)					
Image-Guided Catheter Placement + Aspiration (Surgical Group Only)		X									
Post catheter placement CT scan		X									
rt-PA admin. (Surgical Group Only; Q8h up to 9 doses)		X	X	X							
MTI-M3 specimen collection		X	X	X	X						
Daily CT Scan		X§	X	X	X (Day 4)		X†		X†		
		obtain a CT 24 h post catheter removal on any of these days									
Vital Signs		X	X	X	X						
Neurocheck		X	X	X	X						
Lab Assessments*	X	X	X	X	X						
Concomitant treatments	X	X	X	X	X	X	X	X	X	X	X
NIHSS	X					X	X		X		X
Barthel Index	X						X	X	X	X	X
Modified Rankin Scale	Historic						X	X	X	X	X
Stroke Impact Scale							X		X		X
GOS-E Scale							X		X		X
Mini-Mental Exam							X		X		X
Euro-Quol-5D Scale							X	X	X	X	X
PBSI							X		X		X
Personal Health Utility Assessment Interview									X		
CES-D									X		

\*Assessments should be performed daily through Day 6 regardless of treatment assignment.

†An MRI is an acceptable substitute for this CT scan with Coordinating Center approval.

§Subjects enrolled to medical management: The Day 1 CT scan does not need to be repeated if enrollment occurs on the same calendar day as the stability CT scan (done 6h post the diagnostic CT scan).

## 6.2 Timing of Evaluations

### 6.2.1 Screening/Baseline.

Screening/Baseline is the start of the screening process and begins when the study team is notified of a potentially eligible subject. If any of the assessments required to determine eligibility (stability CT scan, pregnancy test, serum lab assessments) are not part of routine patient management, then these assessments will be listed in the consent form as trial-related procedures and informed consent will be obtained prior to determining eligibility for the trial. The prospective subject will be informed as part of the consent discussion that the screening procedures will determine eligibility for the trial and that signing the consent form does not constitute enrollment into the trial.

### 6.2.2 Day 1 through Day 6

The acute phase of the protocol is defined as day one (day of randomization) through day six post randomization. All subjects randomized to the surgical intervention plus rt-PA will receive up to nine doses of intracatheter injections of rt-PA. Dosing will be discontinued prior to nine doses if an endpoint is satisfied.

Randomization should occur as close as possible to the time that all eligibility criteria are met. If randomization is postponed to accommodate scheduling (i.e., it is preferable to wait until 6 am to randomize instead of midnight), obtain a CT scan to re-confirm stability of the ICH and re-confirm blood pressure stability prior to randomization. For those subjects randomized to surgery (MIS+rt-PA) the surgical procedure should be initiated as close as possible to the time of randomization.

### 6.2.3 Day 7 through Day 365

The follow-up phase of the protocol begins on day 7 and continues through the 12-month follow-up visit.

### 6.2.4 Intervention Discontinuation Evaluations

Subjects withdrawn early from treatment or who withdraw consent or are lost to follow-up will not be replaced. If a subject is withdrawn early from treatment due to a clinical safety endpoint, we expect standard clinical judgment to be applied to continue to monitor the subject until resolution of the event including but not limited to repeat CT scans and repeat laboratory assessments.

**Discontinuation of drug administration and catheter removal.** rt-PA injections will continue as defined by the protocol until an endpoint of clot lysis is reached (i.e., clot is reduced to 10-15 mL or nine doses are administered, whichever

comes first) or an adverse treatment endpoint occurs, such as symptomatic hemorrhage. ICH clot resolution of 10-15 mL will be estimated by comparing the daily dosing CT scans and performing the ABC/2 measurement on sequential scans. A CT scan must be done one day after the catheter is removed to monitor for new bleeding or bleeding extension. After last dose the catheter will be closed for one hour and then reopened to drain for 24 hours to allow for complete removal of rt-PA. The catheter must be closed at the time of removal to avoid pneumocephalus.

A subject will have rt-PA administrations discontinued for any of the following reasons:

- 1) The ICH volume is reduced to less than or equal to 10 mL (surgical endpoint).
- 2) The subject receives nine doses of rt-PA (surgical endpoint).
- 3) Clinically significant rebleeding (treatment failure).
- 4) Uncontrolled coagulopathy defined as INR > 1.4 (treatment termination).
- 5) In the investigator's judgment, withdrawal from the trial would be in the patient's best interest (treatment failure).
- 6) The patient withdraws consent.

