After placement of the catheter and a CT scan to confirm correct placement, a six-hour post-surgical stabilization period is required prior to first injection of rt-PA. Keep the drainage system to drainage for six hours post catheter placement *prior* to first dose of rt-PA. This time is mandated to reduce the possibility of secondary hemorrhage. If new bleeding or bleeding expansion is seen on the post-op CT scan, wait 12 hours and repeat the CT scan. When the bleeding is stable, dosing can be initiated.

If post-operative clot volume is 10 to 15 mL, rt-PA should not be given. The catheter should remain in place and open to drainage for 24-36 hours prior to removal.

**Catheter adjustment/replacement:** Correct catheter placement will be CT-confirmed locally and post-operative measurements will be repeated centrally by the Surgical Center. Catheter adjustments will be made at this time, if necessary. If the hematoma appears larger or the shape is altered on CT scan after the catheter is placed, the catheter may require repositioning and a post-repositioning CT scan to confirm correct placement within the clot as well as stability of clot size. Repositioning is defined as the partial removal or “pull back” of the non-optimally placed catheter. Replacement is defined as removal of the catheter and replacement with a better targeted catheter using the introducer method described above with either the same or a different trajectory of insertion. There is a one-time allowance for a new rigid cannula placement. Soft catheter placements or replacements, usually done through an existing burr hole and always done using a stylet with image guidance, do not count against this limited number of rigid cannula passes. There is no limit to the number of soft catheter placements or replacements as long as stability requirements are met. Occasionally it may be necessary to create a new burr hole/trajectory to access the clot. This will be done only after consultation with the Surgical Center. Repeat CT scan and upload DICOMs of the final catheter placement in the clot into the EDC for Surgical

Center review and approval of catheter location in residual hematoma prior to dosing.

The catheter is then tunneled subcutaneously, connected using sterile technique to a three-way stopcock and then to a closed drainage system. Level the drainage bag to zero.

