**Dosage.** The drug will be administered as a sterile solution and in a sterile manner every 8 ( $\pm$  2) hours for up to 9 doses. The total volume of injectate will equal 1.0 mg rt-PA @ 1 mg/mL plus at least 3 mL of flush or as much flush is needed for the rt-PA to clear the catheter tubing.

**Dosing schedule allowances.** There is a two (2) hour window on either side of the eight (8) hour dosing schedule to allow for scheduling problems, stability determination, INR correction, or any other concern the PI may have regarding giving the dose on schedule. This schedule adjustment should be used as infrequently as possible to maintain a Q8hr schedule for dosing consistency.

**Holding a dose.** If a dose must be held or delayed more than 10 hours to correct an INR value above 1.4 (or other coagulopathy), hold the next scheduled dose, institute corrective therapy and re-assess the INR. Once INR is corrected, dosing may be resumed keeping to the original dose count. If the INR remains > 1.4, continue corrective therapy as required and the investigator may discontinue dosing.

In the event of severe or life-threatening anaphylaxis or hypersensitivity reaction, the treatment phase would be discontinued. The patient would not be retreated with rt-PA. A description of the reaction would be added to the patient's medical record as a serious adverse event for future reference.

**Dosing decision-making by CT.** Before initial dosing and subsequently after every three (3) doses (daily), the investigator is required to view the most recent CT scan to measure clot size and compare to the prior day's scan in order to decide continuation or discontinuation of dosing. As clot size decreases and approaches the target reduction, the next CT may be obtained earlier than after three doses. This process allows the PI and team to confirm that: 1) remaining clot is greater than 10 mL, 2) the blood clot is in direct contact with the catheter, and 3) that the catheter is placed in the clot to be dissolved. Bone windows must be done when obtaining any CT scan in order to confirm that the catheter side ports have contact with the clot. If none of the side ports are in contact with the clot, drug should not be given. Partial contact with the clot should be reviewed by the PI on a daily basis, prior to further dosing.

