## 8 CRITERIA FOR INTERVENTION DISCONTINUATION

rt-PA administration will be discontinued for any of the following reasons:

1. Dosing will be discontinued when the ICH clot volume is reduced to less than or equal to 10 mL, or the subject receives 9 doses of rt-PA (treatment endpoint), whichever occurs first.
2. Dosing will not be started if the ICH clot volume is reduced to less than or equal to 10 mL by clot aspiration alone during catheter placement (surgical endpoint).
3. The subject experiences a clinically significant bleeding event (local or systemic) (treatment failure).
4. In the investigator’s judgment, withdrawal from the trial would be in the subject’s best interest (treatment failure).
5. The subject or legal representative withdraws consent.

All subjects will be followed by the site team through day 365 (reasons 1 to 5) as part of the outcome assessment for the intervention. The use of the phone and mail will be the main means of maintaining contact after discharge. The subject or legal representative has the right to withdraw consent. At the time of consent withdrawal, the site personnel will discuss with the subject or legal representative the level of their consent withdrawal to determine if they are willing to discontinue study treatment but agree to in-person and by phone follow up visits, disagree to follow up visits but agree to phone contact to determine vital status, or no further contact at all.

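### Protocol 6.2.4 gives two different stopping volumes for rt-PA, so a residual clot above 10 mL and up to 15 mL ends dosing under one and not the other

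*Protocol*

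**What the plan says.** **Stopping rt-PA**

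- Protocol 6.2.4, narrative: injections run until "clot is reduced to 10-15 mL or nine doses are administered", whichever is earlier, unless an adverse treatment endpoint occurs. The measurement is also specified: "ICH clot resolution of 10-15 mL will be estimated by comparing the daily dosing CT scans".
- Protocol 6.2.4, numbered list, item 1: "The ICH volume is reduced to less than or equal to 10 mL (surgical endpoint". None of the list's other reasons is a clot volume.
- Protocol 8, item 1: "Dosing will be discontinued when the ICH clot volume is reduced to less than or equal to 10 mL", or at nine doses, whichever is earlier.
- Protocol 5.1.3, dosing decisions by CT: before the first dose and after every three doses the team confirms that "remaining clot is greater than 10 mL", together with two conditions on catheter-clot contact. Near the target, "the next CT may be obtained earlier than after three doses".

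**Starting rt-PA**

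- Protocol 5.1.2: "If post-operative clot volume is 10 to 15 mL, rt-PA should not be given".
- Protocol 8, item 2: "Dosing will not be started if the ICH clot volume is reduced to less than or equal to 10 mL by clot aspiration alone". The 5.1.2 rule is not repeated there.

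**Related figures**

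- Protocol 10.3.3 counts drainage as technically complete below 15 cc.
- SAP 5.6 uses a target of 15 mL or less when it defines treatment failure.
- SAP 5.4 names both 15 mL and 10 mL as protocol thresholds.
- SAP 2.2 places end of treatment (EOT) 24 hours after the last dose.

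**The concern.** The narrative and the list in 6.2.4 both set out to say when injections end, and they give different volumes. Two sites looking at the same CT could each follow the protocol's words, one stopping the drug and the other continuing it. That bears first on subject safety, because the drug is a thrombolytic delivered into the hematoma.

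It also bears on adherence. Protocol 5.4 has compliance reported to the DSMB by center, and in this band there is no single standard to judge it against.

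The analytic consequence is narrower. EOT depends on the last dose, so the choice of stop rule can move the end of the clot-exposure window in SAP Secondary Analysis 3. Protocol Analysis 2b also examines EOT volume at cut-points that include 10 and 15 mL, the two edges of the disputed band.

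**Working it through.** **Step 1. Where the stop rules disagree.** Apply each to the same residual volume, with fewer than nine doses given and no adverse endpoint.

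| Residual clot | 6.2.4 narrative | 6.2.4 list and Section 8 item 1 | Agree? |
|---|---|---|---|
| 8 mL | endpoint passed, stop | stop | yes |
| 10 mL | stop | stop | yes |
| 12 mL | stop | volume criterion not met | no |
| 15 mL | stop | volume criterion not met | no |
| 18 mL | endpoint not met | volume criterion not met | yes |

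The conflict is confined to volumes above 10 mL and up to 15 mL.

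**Step 2. Does any text rank the rules?** Section 8 and 5.1.3 repeat the 10 mL figure without saying that it overrides the narrative. Protocol 5.1.2 and 10.3.3 and SAP 5.6 use figures reaching 15 mL, and SAP 5.4 lists both. Protocol 6.2.2 stops dosing when an endpoint is met but gives no volume. Nothing sets precedence.

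**Step 3. Size for one subject.** Inputs: 1.0 mg every 8 hours, at most nine doses, CT after every three doses (Protocol 5.1.3); EOT 24 hours after the last dose (SAP 2.2). With the first dose at hour 0, dose *k* falls at 8 × (*k* − 1) h and EOT at 8 × (*k* − 1) + 24 h.

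| Last dose | Time given | EOT | Cumulative rt-PA |
|---|---|---|---|
| 3 | 8 × 2 = 16 h | 16 + 24 = 40 h | 3 mg |
| 6 | 8 × 5 = 40 h | 40 + 24 = 64 h | 6 mg |
| 9 | 8 × 8 = 64 h | 64 + 24 = 88 h | 9 mg |

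Suppose the CT after dose 3 shows 12 mL. Under the narrative, dose 3 is the last.

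- If the 10 mL criterion is used and the CT after dose 6 shows 10 mL or less: up to 6 − 3 = 3 further doses (3 mg), and EOT 64 − 40 = 24 h later.
- If the clot stays above 10 mL throughout: up to 9 − 3 = 6 further doses (6 mg), and EOT 88 − 40 = 48 h later.
- If 12 mL is first seen after dose 6 and the clot then stays above 10 mL: up to 9 − 6 = 3 further doses (3 mg), and EOT 88 − 64 = 24 h later.

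The ±2-hour dosing window is not compounded, because 5.1.3 asks that it be used sparingly. The clock here starts at the first dose, whereas Secondary Analysis 3 starts at ictus, so only the differences carry over.

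**Step 4. The start rule.** Read together, 5.1.2 (10 to 15 mL) and Section 8 item 2 (10 mL or less) withhold rt-PA at every post-operative volume up to 15 mL. The gap is that 5.1.3 and Section 8, read without 5.1.2, do not exclude a first dose at, say, 12 mL. No dose count or EOT shift is claimed for this part.

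**The case against.** The strongest reply is that the texts can be read cumulatively. The 6.2.4 list gives sufficient reasons to stop and does not order dosing to continue above 10 mL; the 5.1.3 check is a condition for dosing, not an instruction to dose. On that reading, stopping at 12 mL breaches nothing. A related reading treats 10-15 mL as a target range and 10 mL as the mandatory stop. One can also argue that the narrative defers to rules set elsewhere in the protocol, and that Section 8, being the section on discontinuation criteria, supplies them.

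These readings are possible, but none is written down. Section 8 item 1 pairs its volume with the nine-dose cap and stops at the earlier of the two. That is a complete stop rule parallel to the narrative's, with a different number. If 10-15 mL already ended dosing, the 10 mL criterion would have little left to do. The narrative also defines its endpoint itself and says how to measure it, so it does not simply defer.

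Other points on that side stand:

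- The start texts can be reconciled by reading them together, so that part is secondary.
- Surgical Center guidance and central image review (Protocol 10.3.3 and 10.3.9) may reduce variation, and the Manual of Operations and Procedures, which is not available here, may settle the matter.
- Bringing the CT forward reduces the extra doses.
- EOT already varies between subjects by design, and no bias in Secondary Analysis 3 has been shown.

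**Conclusion.** The concern holds. For residual clot above 10 mL and up to 15 mL, Protocol 6.2.4 contradicts itself on when rt-PA ends, and neither document says which rule governs.

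For a subject at 12 mL after dose 3, the upper bound is 3 or 6 further doses and an EOT 24 or 48 hours later. This assumes the 8-hour schedule, CTs only after every third dose, and no other reason to stop. These are limits on what the volume criterion leaves unstopped, not expected values.

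How many subjects would fall in the band cannot be derived, because on-treatment volume distributions are not given. The mean EOT volume of 18 ± 14 mL in MISTIE II Stage 2 surgical subjects (Protocol 2.2, Table 3) suggests the band is not remote, but gives no count.

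The primary comparison of mRS at 365 days by randomized arm is not directly affected. The mismatch itself is certain; its practical effect is less so. It should be corrected.

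**What to change.** Reconcile Protocol 5.1.2 (post-operative volume), 5.1.3 (dosing decisions by CT), 6.2.4 (the narrative, its CT-estimation sentence and the list) and Section 8 items 1 and 2. One start rule and one stop rule, chosen by the trial's clinical leadership, should appear in identical words in each place. State what the 10-15 mL range means, what the 10 mL figure means, and which governs dosing. Then check the 15 mL goal in Protocol 10.3.3 and the thresholds in SAP 5.4 and 5.6 against that statement. This review takes no view on which volume is right.

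The cost is a protocol clarification with IRB or ethics review (Protocol 11.1) at approximately 90 to 100 centers, plus a notice to sites. Data collection and the SAP analyses do not change.

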### 4.2 Exclusion Criteria

4.2.1 Infratentorial hemorrhage.

4.2.2 Ruptured aneurysm, arteriovenous malformation (AVM), vascular anomaly, Moyamoya disease, hemorrhagic conversion of an ischemic infarct, recurrence of a recent ( $< 1$  year) hemorrhage, diagnosed with radiographic imaging.

4.2.3 Patients with unstable mass or evolving intracranial compartment syndrome.

4.2.4 Irreversible impaired brain stem function (bilateral fixed, dilated pupils and extensor motor posturing), GCS  $\leq 4$ .

- 4.2.5 Thalamic bleeds with apparent midbrain extension with third nerve palsy or dilated and non-reactive pupils. Other (supranuclear) gaze abnormalities are not exclusions. Note: Patients with a posterior fossa ICH or cerebellar hematomas are ineligible.
- 4.2.6 Intraventricular hemorrhage requiring treatment for IVH-related (casting) mass effect or shift due to trapped ventricle. EVD to treat ICP is allowed.
- 4.2.7 Platelet count < 100,000; INR > 1.4.
- 4.2.8 Any irreversible coagulopathy or known clotting disorder.
- 4.2.9 Inability to sustain INR  $\leq$  1.4 using short- and long-acting procoagulants (such as but not limited to NovoSeven, FFP, and/or vitamin K).
- 4.2.10 Subjects requiring long-term anti-coagulation are excluded. Reversal of anti-coagulation is permitted for medically stable patients who can realistically tolerate the short term risk of reversal. Patient must not require Coumadin (anticoagulation) during the first 30 days, and normalized coagulation parameters must be demonstrated, monitored closely and maintained during the period of brain instrumentation.
- 4.2.11 Use of Dabigatran, Apixaban, and/or Rivaroxaban (or a similar medication from the similar medication class) prior to symptom onset.
- 4.2.12 Internal bleeding involving retroperitoneal, gastrointestinal, or genitourinary site or respiratory tract bleeding.
- 4.2.13 Superficial or surface bleeding, observed mainly at vascular puncture and access sites (e.g., venous cutdowns, arterial punctures, etc.) or site of recent surgical intervention.
- 4.2.14 Positive urine or serum pregnancy test in pre-menopausal female subjects without a documented history of surgical sterilization.
- 4.2.15 Allergy/sensitivity to rt-PA.
- 4.2.16 Prior enrollment in the study.
- 4.2.17 Participation in a concurrent interventional medical investigation or clinical trial. Patients in observational, natural history, and/or epidemiological studies not involving an intervention are eligible.

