- 6.3.10 **Vital Signs:** Monitoring of vital signs includes documentation of blood pressure and ICP (if monitored).. Vital signs are to be collected once every six hours beginning at randomization through day six.

- 6.3.11 **Therapy Intensity Levels (TILs):** In addition, therapy intensity levels will be documented at Baseline and day seven. The TILs will be used to document the management intensity of reversal of anticoagulation, Glasgow coma score, blood pressure, temperature, blood glucose, ICP, and cerebral herniation.

All vital signs and TIL data must be recorded in the medical record, or as ICU monitor print outs as source documentation.

- 6.3.12 **Neurocheck:** GCS may be assessed clinically as frequently as every hour. For the purposes of neuromonitoring, GCS will be recorded once every six hours to assess for neuroworsening or clinical improvement. An unscheduled CT scan should be done if the subject improves or worsens by more than two points on the GCS motor scale that is sustained for at least eight hours, or sooner if clinically indicated.

- 6.3.13 **Lab Assessments:** The results of daily white blood cell count, serum glucose, platelet count, aPTT, and INR will be reviewed and recorded in the EDC. These lab assessments will be monitored through day six. The following lab assessments must be done and reviewed to screen the patient for eligibility: platelet count, INR, and, if applicable, urine or serum pregnancy test. The INR must remain  $\leq$  1.4 during dosing.

All lab results and sampling dates and times must be recorded in the medical record as source documentation.

- 6.3.14 **Concomitant treatments:** All concomitant medications administered that are inclusive of the drug classes of interest and procedures performed (randomization through day 6) will be recorded on the eCRF. Drug classes of interest include but are not limited to: anti-hypertensives, sedatives, hypnotics, hematologic modifiers, antiplatelet and anticoagulant medications, antibiotics and any other medication used to treat a neurological adverse event or any serious adverse event. Medications used to treat a neurological adverse event or any serious adverse event will be recorded on the eCRF through day 365.

- 6.3.15 **NIHSS.** The NIHSS should be done by a certified examiner as close to the time of randomization as possible, at day seven, and again at months one, six, and 12.

The NIHSS results may be recorded directly on the electronic case report form.

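### Protocol 6.2.4 ends rt-PA at any INR above 1.4; section 5.1.3 holds, corrects and allows resumption at the same cut-off, and section 8 has no INR item

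*Protocol*

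**What the plan says.** Protocol 6.2.4 gives six reasons for ending rt-PA, under an instruction that it will be ended if any of them applies. Item 4 is "Uncontrolled coagulopathy defined as INR > 1.4 (treatment termination"). The item contains no repeat test, no duration and no condition that correction has failed.

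Protocol 5.1.3 handles the same cut-off in steps. Doses are due every 8 hours, with 2 hours' leeway either side "to allow for scheduling problems, stability determination, INR correction, or any other concern the PI may have regarding giving the dose on schedule". If correction would push a dose past 10 hours, the next scheduled dose is held, corrective therapy is given and the INR is re-assessed. Then: "Once INR is corrected, dosing may be resumed keeping to the original dose count". If correction fails: "If the INR remains > 1.4, continue corrective therapy as required and the investigator may discontinue dosing".

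Protocol section 8 opens with "rt-PA administration will be discontinued for any of the following reasons" and gives five reasons. None mentions INR or coagulopathy. The nearest is investigator judgment, which carries the label of treatment failure rather than treatment termination.

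Two other sections bear on this. Section 6.3.13 sets daily laboratory review ("The results of daily white blood cell count, serum glucose, platelet count, aPTT, and INR will be reviewed and recorded in the EDC") and adds that "The INR must remain" at or below 1.4 during dosing. Section 4.2.10 admits some patients who had been anticoagulated: "Reversal of anti-coagulation is permitted for medically stable patients who can realistically tolerate the short term risk of reversal".

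**The concern.** A stopping rule for an intraclot thrombolytic should have one meaning. Here the value that starts a hold-and-correct procedure in one section is, by definition, a mandatory end of treatment in another. The third section, where a site would look for discontinuation criteria, does not mention it.

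The situation is foreseeable. Patients can enter after reversal of anticoagulation, section 4.2.10 requires their coagulation to be kept normal while the catheter is in use, and the INR is reviewed daily.

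Two things are at stake. A site that follows 6.2.4 to the letter would end lysis in a patient whose INR was readily corrected. A site that resumes under 5.1.3 could be recorded as having deviated from 6.2.4. Section 10.3.10 requires deviations to be reported within 24 hours, section 5.4 sends compliance by center to the DSMB, and section 10.3.6 has the data-capture system detect protocol variances. Each of these needs a single rule to measure against.

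**Working it through.** The plan gives no figure to reproduce. The check is a comparison of the three sections for each state a patient can be in, followed by simple dose arithmetic.

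| Patient state | 6.2.4 item 4, read literally | 5.1.3 | Section 8 |
|---|---|---|---|
| INR above 1.4, correction under way | rt-PA must end | use the dosing window, or hold the dose and correct | no INR item |
| INR was above 1.4, now corrected | rt-PA has already ended; no route back | dosing may resume | no INR item |
| INR still above 1.4 after correction | rt-PA must end | investigator may end it | no INR item; investigator judgment only, labelled treatment failure |

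- Row 1: 6.2.4 leaves no room for the correction time that 5.1.3 provides. The longest interval before the hold rule applies is 8 + 2 = 10 hours.
- Row 2: this is the substantive conflict. The resumed dose is permitted by 5.1.3 and contrary to a literal 6.2.4.
- Row 3: the sections differ on whether stopping is mandatory. The dosing consequence is small, because 5.1.3 and 6.3.13 together allow no dose while the INR is above 1.4. What remains is whether the patient is formally discontinued or on hold, and whether a late correction could reopen dosing.

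**Size in one patient.** Inputs from 5.1.3 and 6.3.13: 1 mg per dose, at most nine doses, dosing every 8 hours (three a day), daily INR. Assumption: exactly one dose is held. Let k be the number of doses given when the raised INR is found.

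- Total under literal 6.2.4 = k mg.
- Ceiling under 5.1.3 = 9 − 1 = 8 mg if the held dose counts toward the nine, or 9 mg if it does not. The text on keeping the original count does not settle which.
- k = 3: 8 − 3 = 5 mg, or 9 − 3 = 6 mg. Difference 0 to 5 mg, or 0 to 6 mg.
- k = 6: 8 − 6 = 2 mg, or 9 − 6 = 3 mg. Difference 0 to 2 mg, or 0 to 3 mg.

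The lower end is 0 because resumption is optional. The upper ends are ceilings, because dosing also stops once the clot is 10 mL or less.

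**Frequency.** None can be derived. Appendix 5 lists coagulopathy and increased PT at 0.17% each of 573 phase II events. Since 573 × 0.0017 ≈ 0.97, that is about one event each. These are shares of adverse events, not a per-patient rate of INR above 1.4.

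**The case against.** The strongest reply is that the sections can be read together. At an INR of 1.3 the patient is no longer above 1.4, so item 4 is not met when dosing resumes. Treating a corrected value as a permanent stop leaves the word uncontrolled with no work to do. Section 6.2.4 also says that injections proceed as the protocol defines, which brings in 5.1.3. Exclusion 4.2.9 uses the same cut-off with correction built in.

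This is probably what was intended, but it is not what item 4 says. The item defines its term by the INR value alone. The exclusion criteria show the protocol can draw the distinction: 4.2.7 excludes on the value, and 4.2.9 separately excludes on failure to sustain correction. Item 4 takes the form of 4.2.7. Even on the kinder reading, mandatory versus optional stopping is unresolved for a persistently high INR, and section 8 still omits the criterion. That omission alone is an editorial gap, since section 8 does not claim to be exhaustive.

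A second reply stands in full. A reader might infer that the defect is that two sites can treat the same corrected patient differently. The documents do not support that as the fault: 5.1.3 makes resumption optional, and both discontinuation lists include investigator judgment. That variation would exist without item 4 and would survive the fix.

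A third reply stands in part. Nothing shows that a resumed dose would in practice be logged as a deviation. Section 9.2 assigns a central monitor to review drug-administration deviations, and the detailed administration steps are in a manual not available here. Miscounting is possible, not demonstrated.

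**Conclusion.** The point holds as a minor error in an operative dosing rule. Section 6.2.4 item 4 mandates a stop at a value for which 5.1.3 prescribes correction and permits resumption, and section 8 does not name the criterion. A resumed dose therefore complies with one section and breaches another.

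The per-patient difference is at most 5 or 6 mg if the raised INR is found after dose 3, and 2 or 3 mg after dose 6, given one held dose; it may be zero. That few patients are affected is a judgment, because the documents give no per-patient rate.

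Two further inferences should be resisted. The protocol does not allow rt-PA at an INR above 1.4 under any section. Nor is the primary analysis altered: SAP 5.2 analyzes subjects by assigned arm, and the conflict touches no sample size, power or error rate. Section 10.4.3 also requires the circumstances of every early stop to be documented, whatever the reason.

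**What to change.** Three text edits to the protocol:

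1. Section 6.2.4 item 4: replace with *INR that remains > 1.4 after the hold-and-correct step in 5.1.3 (treatment termination)*.
2. Section 5.1.3: for an INR that stays above 1.4 after that step, change *may discontinue* to *will discontinue*.
3. Section 8: add the same criterion with the same treatment-termination label.

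Optionally, state in 5.1.3 whether a held dose counts toward the nine.

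The edits leave resumption in a corrected patient to the investigator, as now, and remove the ground for calling it a deviation. They add no procedures, visits or patients. The only discretion lost is an open-ended hold at a persistently high INR, including the chance of reopening dosing after a late correction. No dose could be given during such a hold in any case.
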